6.7.2. Other Analyses

Mean percentage changes from baseline in supplemental oral calcium and supplemental calcitriol dosage at each visit

The absolute and percentage changes from baseline will be summarized at each visit. No formal statistical test will be done.

Proportion of subjects achieving the primary endpoint at each visit

The number and percentage of subjects achieving the primary efficacy endpoint will be presented by visit. No formal statistical test will be done.

Mean percentage change from baseline in 24-hour urine calcium excretion

The absolute and percentage changes from baseline will be summarized by visit. No formal statistical test will be done.

Impact of calcium source (carbonate vs. citrate) on response

The number and percentage of subjects meeting the criteria of being responders will be presented by visit and by calcium source (carbonate vs. citrate). No formal statistical test will be done.

Impact of calcium-sparing diuretics on serum and urinary calcium

The number and percentage of subjects who use at least one calcium-sparing diuretics during the study will be presented.

The urinary calcium will be listed for subjects who received calcium-sparing diuretics during the study. No formal statistical test will be done.

Proportion of subjects that maintain a calcium phosphate product in the range of 35 to 55 mg²/dL²

Calcium phosphate product will be classified as normal (35 - 55 mg²/dL²), or abnormal (including low and high). The number and percentage of subjects with maintenance of a calcium phosphate product in the normal range will be presented by visit. No formal statistical test will be done.

Distribution of subjects by rhPTH[1-84] doses at the End of Treatment Visit

The number and percentage of subjects at different dose levels at the EOT visit will be summarized. No formal statistical test will be done.

Change from baseline in bone turnover markers (bone-specific alkaline phosphatase, serum carboxy-terminal telopeptide of type I collagen, serum procollagen type I amino-terminal propeptide, and osteocalcin), PTH and ECP antibodies, and BMD by DXA

The absolute and percentage changes from baseline will be summarized by visit. No formal statistical test will be done. For DEXA, Z-scores will also be presented and summarized.

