- Adjustment of supplemental calcium and calcitriol regimens will be based on serum calcium levels, with the goal to be a reduction or removal of calcitriol treatment to the maximum degree clinically possible and to decrease the prescribed oral calcium supplementation to  $\leq 500$  mg daily.
- Subjects will have blood draws to assess total serum calcium levels (which may be performed locally) 3 to 5 days after ANY dose adjustment of rhPTH[1-84], after any significant change in doses of calcium and/or and calcitriol supplements, or at any other time

at the discretion of the investigator. Results of local total serum calcium levels will be recorded in the source document.

[figure not shown]
- Once a subject achieves a stable serum calcium (target: between 8.0 and 9.0 mg/dL) with the minimum doses of supplements possible, they will be maintained at that dose of rhPTH[1-84].
- If ANY predose (trough) total serum calcium is > 11.9 mg/dL study drug will be stopped. Once total serum calcium returns to the normal range, rhPTH[1-84] can be reintroduced. The rhPTH[1-84] dose may be maintained at the previous level if reductions in oral calcium supplements and/or calcitriol are possible. If oral calcium supplements have been previously reduced to ≤ 500 mg daily and calcitriol has been eliminated, then rhPTH[1-84] should be reintroduced at the next lowest dose level and supplemental oral calcium and calcitriol should then be adjusted accordingly to obtain a predose total serum calcium level of approximately 8.0 to 9.0 mg/dL.
- If the predose total serum calcium level remains above 10.0 mg/dL for two or more safety assessments or study visits on normal dietary intake and study drug alone, then the rhPTH[1-84] dose may be reduced to the next lowest dose level and supplemental oral calcium and calcitriol then adjusted accordingly to obtain a predose total serum calcium level of approximately 8.0 to 9.0 mg/dL. Study medication will be stopped if the predose total serum calcium remains above the upper limit of the laboratory normal range (ULN) for two or more safety assessments or study visits (no more than 5 days apart) at the lowest dose regimen, following withdrawal of all supplementary oral calcium and calcitriol therapy. Further choices on adaptation of treatment regimens, reinstitution of previous therapy, or discontinuation from study will be made in consultation with the Shire medical monitor.

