#### **4.4 Subject Withdrawal Criteria**

All subjects are free to withdraw from participation in this study at any time, for any reason, specified or unspecified without prejudice to subsequent care. Withdrawn dosed subjects will not be replaced. A subject may be withdrawn from the study under any of the following circumstances:

- Withdrawal of informed consent
- If, in the opinion of the investigator, Institutional Review Board/Independent Ethics Committee/Research Ethics Board (IRB/IEC/REB), Health Authority and/or Shire, it is no longer in the subject's best interest to continue in the study
- Subject no longer meets all inclusion criteria or meets any criterion for exclusion
- Lack of compliance with study procedures or study drug administration, as determined by the investigator
- Occurrence of an SAE determined by the investigator to be possibly related to study drug and not alleviated with treatment of symptoms
- Adverse event
- Hypersensitivity determined by the investigator to be possibly related to study drug
- Pregnancy or lactation
- Administrative reasons
- Treatment with commercial drug (Natpara)

In all cases, the reason for withdrawal must be recorded in the subject's medical records. If the reason is not known, the subject must be followed up to establish whether the reason was an AE and, if so, this must be reported in accordance with the procedures described in Section [6.2.1](#).

As far as possible, all examinations scheduled for the end-of-study evaluations must be performed on all subjects who participate but do not complete the study according to protocol.

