### **8.6.2 Handling of Dropouts or Missing Data**

No safety data will be imputed. The missing patterns of the efficacy variables will be assessed and an unbiased imputations method will be documented in the SAP.

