2.2. Secondary objective

- To evaluate the impact of different preparations of calcium on the response to rhPTH[1-84] replacement therapy
- To demonstrate that dosing with rhPTH[1-84] across a dose range of 25 to 100 µg SC can be implemented in a safe and effective manner and can be maintained throughout long-term treatment
- To evaluate the impact of calcium-sparing diuretics on serum and urinary calcium

3. Study Design

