3.4.2. Changes from Analyses Planned in the Protocol

No changes from protocol specified analyses are planned.

4. Efficacy and Safety Variables

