6.7.5. Sensitivity Analyses

There is no sensitivity analysis planned for this study.

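### The SAP lacks the missing-data method the protocol promises for efficacy, so late by-visit means describe only subjects still on study and cannot alone show a maintained effect

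*SAP*

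**What the plan says.** Protocol 8.6.2 makes a commitment: "The missing patterns of the efficacy variables will be assessed and an unbiased imputations method will be documented in the SAP". Protocol 8.8 adds that changes to the planned analyses go into the SAP. SAP 3.4.2 states "No changes from protocol specified analyses are planned", and SAP 6.7.5 states "There is no sensitivity analysis planned for this study".

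SAP 5.4.1 has the matching heading on dropouts and missing efficacy data, but its content is the derivation of calcium and vitamin D doses. Missing diary doses are not imputed, and an interval needs at least 9 recorded days. One sentence deals with subjects who stop early: as written, it excludes them from the post-baseline prescribed dose, which SAP 6.7 makes the primary dose source. Nothing is said about urine calcium, bone markers, BMD or response status after a subject leaves.

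SAP 6.7.2 then summarises by visit. For supplement dose: "The absolute and percentage changes from baseline will be summarized at each visit". For response: "The number and percentage of subjects achieving the primary efficacy endpoint will be presented by visit". SAP 5.1 defines an end-of-treatment (EOT) value as the last on-treatment measurement, and SAP 6.7 shows it as a separate time point. SAP 6.1 reports the number assessed at each planned visit and the reasons for discontinuation.

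**The concern.** A secondary objective in SAP 2.2 is to show that dosing across the range is safe and effective and "can be maintained throughout long-term treatment". SAP 6.7 says the by-visit tables are there to show change over time, so they will be read as trajectories. Treatment runs up to 80 months, about 50 subjects are expected, withdrawn subjects are not replaced, and there is no control arm.

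Once a subject leaves, he or she contributes to no later by-visit mean. Protocol 4.4 lists adverse events, poor compliance, administrative reasons and a move to the commercial product among the grounds for withdrawal. Some of these may be related to outcome and others may not. If they are related, a change in who remains can look like a maintained, improving or fading effect. The method promised in protocol 8.6.2 would have addressed this.

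**Working it through.** **1. Commitment against delivery.** Protocol 8.6.2 asks for two things: an assessment of missing patterns and a documented method. SAP 5.4.1, 6.7.2 and 6.7.5 contain neither, and SAP 3.4.2 does not record the omission. This mismatch needs no arithmetic and holds at any dropout rate.

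**2. The plan's own figures.** The documents give no dropout rate, response rate, SD or power calculation. The one relevant figure, the duration in protocol 3.2, reproduces: 80 months + 4 weeks = 80 + 28/30.4 = 80.9, stated as about 81. (The columns of SAP Table 4.3 stop at Month 72, with a note that the schedule then repeats.) All rates below are assumptions.

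**3. Response proportion.** Let q be the share retained, pS the response in stayers and pL the response in leavers. The observed-case figure is pS and the all-treated figure is q·pS + (1−q)·pL, so

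bias = (1−q)(pS − pL).

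With pS = 0.75 and pL = 0.25:
- q = 0.9: 0.1 × 0.50 = +5 points
- q = 0.7: 0.3 × 0.50 = +15 points (75% shown, 60% in all treated)
- q = 0.5: 0.5 × 0.50 = +25 points

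With pL = 0.75 the bias is 0 at every q. With pS = 0.60, pL = 0.80 and q = 0.6 it is 0.4 × (−0.20) = −8 points.

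Bounds for N = 50, with about 75% response in those assessed:

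| Retained | Observed | All leavers non-responders | All leavers responders |
|---|---|---|---|
| 45 | 34/45 = 75.6% | 34/50 = 68% | 39/50 = 78% |
| 35 | 26/35 = 74.3% | 26/50 = 52% | 41/50 = 82% |
| 25 | 19/25 = 76.0% | 19/50 = 38% | 44/50 = 88% |

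The same displayed figure, about 75%, fits increasingly different all-treated results.

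**4. Continuous endpoint.** The simulation used 50 subjects, 40 visits and 1,500 runs. Percentage change in dose started at a mean of −50 (SD 25) and faded by a mean of 20 points (SD 20) to −30 at the last visit, with residual SD 15. The log-odds of leaving at each visit rose by 0, 0.5 or 1.0 per 25 points of less favourable previous value, at three base rates.

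| Dependence of leaving on outcome | Retention | By-visit mean (all-subject mean about −30) | EOT mean |
|---|---|---|---|
| None | 85% / 68% / 49% | −30.3 / −30.1 / −29.8 | −31.7 / −33.5 / −35.5 |
| Moderate (0.5) | 79% / 59% / 40% | −33.7 / −38.1 / −43.3 | −31.4 / −32.9 / −34.9 |
| Strong (1.0) | 68% / 47% / 32% | −40.4 / −48.0 / −54.5 | −31.1 / −32.2 / −33.5 |

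When leaving is unrelated to outcome there is no material bias. With strong dependence and 32% retained, the assumed fading is wholly hidden.

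**5. Does EOT fill the gap?** In these runs EOT was closer to the all-subject mean than the by-visit mean whenever leaving depended on outcome, but it drifted when leaving did not. It fixes each leaver at the time of leaving, so its error depends on how much the effect changes afterwards. It mixes durations and estimates no particular visit.

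**6. Where response can be scored.** Protocol 6.2.3 drops albumin from the routine extension draw. It remains in the Chem-20 panel, scheduled every 12 months and at End of Treatment. The albumin-corrected condition therefore cannot be evaluated as scheduled at most two-monthly visits, and by-visit response in the extension concerns far fewer time points than dose does.

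**The case against.** The primary objective is safety, efficacy is descriptive with no testing, and summaries while on study are common in open-label extensions. Leavers are not absent: EOT retains their last on-treatment value. Attrition is not hidden: SAP 6.1 gives numbers assessed and reasons, and SAP 5.1 gives the number of subjects with each summary. All of this stands. It does not supply the method promised in protocol 8.6.2 or show how leavers' results differed, and the absence of tests does not remove bias from a descriptive mean.

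A reader might infer that late-visit results are biased in the drug's favour. The documents do not support that. A move to the commercial product may be unrelated to response. The rule in protocol 3.1 for calcium persistently above the ULN applies after all supplements are withdrawn, so such a subject meets both supplement-dose conditions while failing the calcium one. Stopping drug under that rule leads to consultation, not automatically to leaving the study.

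A reader might also infer that by-visit proportions cover only stayers. SAP 6.7 assigns all efficacy analyses to the ITT population, and 6.7.2 gives no denominator. The supportable criticism is that the denominator is unstated.

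Lastly, a repeated-measures model is unbiased only if data are missing at random, and counting leavers as non-responders is a convention rather than an unbiased method. Both points stand and limit how the added results may be described.

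**Conclusion.** The concern holds in this form. The SAP omits a missing-data assessment and method that the protocol commits it to, and does not declare the omission. By-visit means describe subjects still on study, and by-visit proportions have no stated denominator. EOT and the disposition table soften this but do not estimate the late-visit effect that the long-term objective needs.

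The bias is a risk of unknown size and either direction. It is near zero if leaving is unrelated to outcome; under the assumptions shown it runs from −8 to +25 points for response. Those figures rest on assumed retention and assumed differences between stayers and leavers. The reading that nothing in the plan keeps or reveals leavers goes too far, as does any claim that bias has been shown. This should be corrected before the final analysis; it does not affect the primary safety objective.

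**What to change.** 1. In SAP 5.4.1 and 6.7.2, beside the observed means, add a likelihood-based repeated-measures model with visit and baseline for supplement dose, urine calcium, bone markers and BMD. Report it with 95% CIs and state the missing-at-random assumption. With about 50 subjects, use yearly visits if needed for convergence.
2. State the denominator of every by-visit proportion. Where albumin-corrected calcium is scheduled, show the observed-case percentage and an all-ITT percentage counting leavers as non-responders, labelled as a lower bound. Show moves to the commercial product separately.
3. Compare baseline values, last values and trajectories of leavers and stayers by reason for leaving. This is the assessment of missing patterns that protocol 8.6.2 asks for.
4. Repair the early-discontinuer sentence in SAP 5.4.1. It follows text about excluding the dose prescribed at the Week 52 or early termination visit and may have been meant to complete it. Read literally, it would also remove leavers' prescribed doses from EOT.

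If no method is adopted, record in SAP 3.4.2 that it was dropped and limit late-visit statements to subjects still on study.

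The cost is SAP wording and a few tables from data already collected, an explicit model assumption, and a less favourable lower-bound response figure beside the observed one.

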- At and any time following the Week 16 (Visit 4), subjects who are on a stable dose of rhPTH[1-84] and have a 24-hour urine calcium > 300 mg (males) and > 250 mg (females) may be treated for hypercalciuria with calcium-sparing diuretics, if this therapy had not been introduced prior to the study. Newly started calcium-sparing diuretics will be given initially at a low dose.
- Monitoring for serum potassium, sodium, and calcium will be performed 1 week and again 1 month following the institution or change in dose of the calcium-sparing diuretic and then at each subsequent scheduled clinic visit.
- Monitoring of urine calcium will be performed at Weeks 16, 32, and 52 (Visits 4, 6, and 9) and every 4 months thereafter. For subjects on calcium-sparing diuretics, further dose adjustment of the diuretic will be done at the discretion of the investigator, based on urinary and serum calcium values.
- During the week following the last visit (End of Treatment or early termination visit), subjects who are discontinuing rhPTH[1-84] treatment (ie, those who are NOT continuing on commercial Natpara) will have oral calcium and/or active vitamin D adjusted to compensate for the cessation of NPSP558 (rhPTH[1-84]). Their total serum calcium levels will be checked locally at an interim visit scheduled 3 to 5 days after the last dose of study medication. Subjects will also be scheduled for a follow-up clinic visit at the end of this week in order to have serum calcium and phosphate checked.

- Subjects who terminate or complete the study and opt to continue treatment on commercial drug (Natpara), where available, will not require follow-up serum calcium and/or phosphate checks as a part of this study, but rather should continue follow-up serum calcium and/or phosphate monitoring by a physician according to approved labeling instructions. These subjects will be contacted one week after end of treatment for a wellness check.
- Approximately 4 weeks (30 days) following the End of Treatment visit, subjects will be contacted by telephone in order to assess AEs/serious AEs (SAEs).

[figure not shown]
A schematic representation of the study design is displayed in [Figure 3-1](#) and [Figure 3-2](#).

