**AND**

- An albumin-corrected total serum calcium concentration that is normalized or maintained compared to the baseline value and does not exceed the ULN of the central laboratory

In addition, the following efficacy variables will be summarized:

- Mean percentage changes from baseline in supplemental oral calcium and supplemental calcitriol dosages at each visit
- Proportion of subjects achieving the first three conditions of the efficacy endpoints defined above, at each visit
- Mean change from baseline in 24-hour urine calcium excretion
- Impact of calcium source (carbonate vs. citrate) on response
- Impact of calcium-sparing diuretics on serum and urinary calcium
- Proportion of subjects that maintain a calcium phosphate product  $\leq 55 \text{ mg}^2/\text{dL}^2$  ( $4.4 \text{ mmol}^2/\text{L}^2$ )
- Distribution of subjects by rhPTH[1-84] doses at the End of Treatment Visit
- Change from baseline in bone turnover markers (BSAP, s-CTx, P1NP, and osteocalcin), PTH antibodies, and BMD by DXA
- Additional subgroup analyses that are specified in the SAP

Note that the baseline parameters for the efficacy variables for the RACE study will be the end of study and baseline parameters from the RELAY or REPLACE studies. The visits will be defined in the SAP. No between-group comparisons with p-values are planned. No statistical testing will be conducted to compare between group differences.

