5.9. Examination of Subgroups

Subgroup analysis by gender will be performed for the primary efficacy endpoint. Additional subgroup analysis may be explored as appropriate. Subgroup results need to be interpreted with caution if there is insufficient number of subjects in a subgroup.

6. Statistical Analysis

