6.8.2. Clinical Laboratory Evaluation

All laboratory parameters will be collected and processed via a central laboratory, with exception of all urine pregnancy tests and total serum calcium levels which will be done at investigator's local laboratories. Standard international (SI) units will be used for data presentation. Only scheduled lab parameters will be included in the lab summaries. All lab data will be included in the listings.

Quantitative results will be summarized for hematology, serum chemistry, thyroid function tests (levothyroxine and thyroid-stimulating hormone), creatinine clearance, urinary chemistries (24-hour urine calcium, phosphate, and sodium excretion), and selected urinalysis parameters (pH, specific gravity, and urobilinogen) by visit. Both actual values and change from baseline will be summarized. Additionally, shift tables will be presented, summarizing cross tabulations of low,

normal, and high based on the parameter normal range, from baseline to each post-baseline visit and EOT. Percentages for shift tables will be based on the number of subjects with both baseline and post-baseline values at each visit.

Categorical urinalysis findings and urine pregnancy results will be presented in appendix data listings only.

Estimated creatinine clearance rate will be re-calculated based on the Cockcroft-Gault (C-G) equation:

$$\text{CLcr (mL/min)} = [140 - \text{age (years)}] \times \text{weight (kg)} \{ \times 0.85 \text{ for female subjects} \} / (72 \times \text{serum creatinine (mg/dL)}),$$

Estimated creatinine clearance rate will be summarized by stages as defined in Table 5.

Table 6.1 Definition of the Stages of Clcr3

Stage	Description	CLcr (mL/min)
1	Control (normal) Glomerular filtration rate (GFR)	≥ 90
2	Mild decrease in GFR	60-89
3	Moderate decrease in GFR	30-59
4	Severe decrease in GFR	15-29
5	End Stage Renal Disease (ESRD)	<15 not on dialysis
		Requiring dialysis

The number and percentage of subjects with post-baseline results qualifying as markedly abnormal will be summarized by parameter. A listing of all values for the parameter which qualifies as markedly abnormal will be provided. Markedly abnormal laboratory criteria are defined in Table 6.

Table 6.2 Markedly Abnormal Laboratory Criteria⁴

Lab parameter	Unit	Lower Limit	Upper Limit
Chemistry			
Albumin	g/L	≤20	≥90
Alkaline Phosphatase	U/L	NA	>2*ULN
ALT	U/L	NA	>3*ULN
Amylase	U/L	≤15	≥350
AST	U/L	NA	>3*ULN
Bilirubin	μmol/L	NA	>2*ULN
BUN	mmol/L	NA	≥10.7

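### The planned outputs for the calcium-sparing diuretic objective, a user count and a urinary calcium listing, do not address it, although the data for a descriptive answer are collected

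*SAP*

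**What the plan says.** The third secondary objective, worded alike in Protocol 2.2 and SAP 2.2, is "To evaluate the impact of calcium-sparing diuretics on serum and urinary calcium". It returns as an endpoint in Protocol 2.3.3 and SAP 4.3. Protocol 8.3 introduces the list that contains it with "In addition, the following efficacy variables will be summarized".

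SAP 6.7.2 gives two outputs under this endpoint. The first is "The number and percentage of subjects who use at least one calcium-sparing diuretics during the study will be presented". The second is "The urinary calcium will be listed for subjects who received calcium-sparing diuretics during the study". It adds that there will be no formal test. SAP 3.4.2 states: "No changes from protocol specified analyses are planned".

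On data collection, Protocol 3.1 says: "Monitoring for serum potassium, sodium, and calcium will be performed 1 week and again 1 month following the institution or change in dose" of the diuretic, and at each scheduled visit after that. The same section sets 24-hour urine calcium at Weeks 16, 32 and 52 and then every 4 months. From Week 16, subjects on a stable rhPTH[1-84] dose whose urine calcium exceeds 300 mg (men) or 250 mg (women) may be given a calcium-sparing diuretic if they were not already on one. Protocol 5.4.1 lets subjects who enter on such a diuretic stay on it, and has medication dates and doses recorded.

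**The concern.** A question about impact needs some contrast: before against after, or users against non-users. The SAP plans neither. Serum calcium, which the objective names, has no output under this endpoint. The user count mixes subjects already treated at entry, who have no pre-start value in this study, with subjects who start on study and do.

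The other exposure-type objective shows that the SAP can do more. In the same section, calcium source (carbonate or citrate) gets responder counts and percentages by visit and by source.

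At stake is one of three secondary objectives. Protocol 1.1 names thiazides among the causes of hypercalcaemia because they lower urinary calcium excretion. The serum half of the question is therefore its safety half, in a study whose primary objective is safety.

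**Working it through.** The documents give no figure for this endpoint to reproduce. The check is a comparison of text, with three short calculations.

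**1. Objective against planned output**

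| Element | Objective, endpoint, Protocol 8.3 | SAP 6.7.2 |
|---|---|---|
| Serum calcium | named | no output |
| Urinary calcium | named | listing only |
| Before/after start, or user/non-user | needed to speak of impact | none |
| Entry users and new starters | both can occur (Protocol 5.4.1, 3.1) | one count |
| Form | summary | user count and listing |

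**2. Does another output fill the gap?** No.
- SAP 5.9 fixes one subgroup: "Subgroup analysis by gender will be performed for the primary efficacy endpoint". Others are optional, and none is defined by diuretic use.
- For laboratory data, SAP 6.8.2 says "Both actual values and change from baseline will be summarized", by visit, with all subjects together. The urine calcium summary in SAP 6.7.2 is also for all subjects.
- Under SAP 5.3.2, baseline for completers of REPLACE or RELAY is that study's baseline. Change from baseline therefore mixes the effects of rhPTH[1-84], supplements and diuretic.
- SAP 6.8.2 keeps only scheduled tests in the summaries, and SAP 5.3.1 uses nominal visits in the extension. The 1-week and 1-month serum draws thus have no defined place in any summary.

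**3. Are the data there?** Scheduled central measurements for a subject followed to Month 72 (Protocol 6.2.3, Tables 6-1 to 6-3):
- 24-hour urine calcium: baseline and Weeks 16, 32 and 52 (4), plus Months 16 to 72 every 4 months (15). 4 + 15 = 19.
- Serum calcium: baseline and Weeks 4, 8, 16, 24, 32, 40, 48 and 52 (9), plus Months 14 to 72 every 2 months (30). 9 + 30 = 39, before the extra draws after diuretic start or dose change.

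**4. How precise could a summary be?** The number of on-study starters, m, is not in the documents. The 95% CI half-width for a mean paired change, in units of the SD of that change, is t(0.975, m − 1)/√m. For assumed values of m out of about 50 subjects:

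| m | 5 | 10 | 15 | 20 | 25 |
|---|---|---|---|---|---|
| half-width (SD) | 1.24 | 0.72 | 0.55 | 0.47 | 0.41 |

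**5. Regression to the mean.** Let E be the excess of the qualifying urine value over the subject group's mean, and r the correlation between any two measurements. The documents give neither. With no drug effect, the expected fall from the qualifying value is E − rE = (1 − r)E. If the qualifying value is averaged with one other pre-start value, it is (E + rE)/2 − rE = (1 − r)E/2. For an assumed r of 0.5 to 0.7, that is 30% to 50% of E with one value and 15% to 25% with two. Averaging halves the artefact and does not remove it.

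**The case against.** The strongest reply is that this is a wholly descriptive extension of about 50 subjects. SAP 5.1 rules out formal testing, and confidence intervals are not among its summary statistics. The number of starters may be small, and a listing is a defensible format for a handful of subjects. The mock tables are in a separate document (SAP section 8), so the listing may already show start dates. Medication dates are recorded, and all laboratory data are listed, so a reader could piece the picture together. A mean change in subjects treated because their urine calcium was high is also open to bias.

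Much of this stands. The lack of a test is no defect, a confidence interval is optional, and the listing should stay. The bias is real, and the fix does not remove it. But small numbers do not explain why serum calcium is left out, and a listing is not the summary that Protocol 8.3 announces.

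A reader might go further and infer two things that the documents do not support. One is that the trial lacks the data to answer the objective; the schedule shows otherwise. The other is that hypercalcaemia in diuretic users would go unreported. SAP 6.8.1 counts subjects and episodes of hypercalcaemia for the whole trial. SAP 6.8.2 gives by-visit chemistry, shift tables, and counts and listings of markedly abnormal calcium (3.0 mmol/L or more). A diuretic user's event would appear there, without being tied to the diuretic.

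**Conclusion.** The planned outputs do not address the objective and fall short of Protocol 8.3, and SAP 3.4.2 does not declare the difference. This affects one of three secondary objectives and leaves the primary safety objective untouched. What is missing is narrow: serum and urinary calcium in relation to diuretic start, with entry users kept apart.

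The conclusion rests on the text alone and needs no assumed figure. The precision table depends on assumed numbers of starters, and the regression fractions on an assumed correlation. Neither is an estimate from this trial. Because the gap is in outputs and the data are collected, it is cheap to close and should be closed.

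**What to change.** In SAP 6.7.2:
- Keep the user count, but split it into subjects on a diuretic at entry and subjects who start on study.
- Keep the listing, and add serum calcium and diuretic start dates.
- Add one descriptive table for on-study starters. For 24-hour urine calcium and serum calcium, give n, mean, median, SD, minimum and maximum before start and at the first and second measurements after start, with the within-subject change. Include the 1-week and 1-month serum draws. Add a 95% CI if numbers allow.
- Use pre-start values taken on RACE treatment where available. For a subject starting soon after Week 16, the only scheduled urine values are baseline, which precedes RACE dosing, and Week 16.
- Show rhPTH[1-84], calcium and calcitriol doses at the same times.
- Show entry users separately, and alongside them subjects above the urine threshold who did not start a diuretic.

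The cost is SAP wording and one table, with no new data collection. State these limits with it:
- The subset is non-randomised, probably small, and of unknown size.
- Starters qualify on high urine calcium, so regression to the mean and concurrent dose changes remain and no causal reading follows.
- No extra urine collection follows diuretic start, so the first post-start urine value may come months later.
- Albumin is not drawn at routine extension visits. Only the yearly panels (Months 24, 36, 48, 60 and 72) include it, so serum calcium at 30 − 5 = 25 of the 30 extension visits to Month 72 is uncorrected and should be labelled so.
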